9.4. Subgroup Analysis

Efficacy variables including annualized HV, HSDS and IGF-1 SDS, demographic and baseline characteristics and TEAE may also be summarized based on the following subgroups.

- Age (< 3 years, ≥ 3 to <6 years. [≥ 6 to <11 years for girls, ≥ 6 to <12 years for boys] and [≥ 11 years for girls, ≥ 12 years for boys])
- Gender
- Asian vs Non-Asian
- Tanner Stage
- US vs. Non-US

For US sites, subjects will be switched from syringe to auto-injector during the study. The following analysis will be repeated for US subjects for auto-injection:

- Exposure/compliance
- TEAEs
- Local Tolerability
- Anti-body (only the positive vs negative)
- Device related PROs

10. Pharmacodynamics Analyses

The Pharmacodynamic (PD) endpoint, Serum IGF-1 SDS will be collected at 5 days \pm 1 day post-dose. Listings will be generated for PD endpoints.

11. Patient-Reported Outcomes

All Patient-Reported Outcomes used in this trial have been assessed for understanding by GHD patients and their parents/legal guardians/caregivers as intended by the Sponsor in a prior Cognitive Debriefing study per the Guidance for Industry. Questionnaire are administered during the study. The following endpoints are also collected:

- Preference for TransCon hGH or commercially available daily hGH treatment
- Satisfaction with daily hGH and weekly TransCon hGH over time

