3.3.3. Pharmacodynamic Endpoints

- Serum IGF-1 SDS at 5 days \pm 1day post-dose

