5.3. Visit Window

The final visit of the parent trial should serve as the first visit (Visit 1) of the extension trial and data collected in the parent trial before the first study treatment will serve as baseline data for the extension trial. After Visit 1, subsequent visits will occur 5 days (± 1 day) post-dose at Week 13 (± 2 weeks) and then every 13 weeks (± 2 weeks) ongoing.

Post-baseline unscheduled visit (occurred after the date of initiation of the first dose) or end of study visit (early termination visit) will be mapped to the post-baseline scheduled visit with the closest target study day for each scheduled assessment according to Table 2. If the unscheduled visit is in the middle of two scheduled visits, map it to the later one. After mapping, if there are more than one visit in the same window, the visit closer to the target assessment day will be used. If more than one visit has the equal distance to the target day then the later one will be used, if more than one visit on the same day, use the time or the sequence number to select the later record. For listings and shift tables, all data points will be included.

Table 2. Analysis Window

VISIT	Week	Target Study Day	Study Day Window
Visit 1	Week 1	1	≤ 1
Visit 2	Week 13	90	2, 135
Visit 3	Week 26	181	136, 226
Visit 4	Week 39	272	227, 317
Visit 5	Week 52	363	318, 408
Visit 6	Week 65	454	409, 499
Visit 7	Week 78	545	500, 590
Visit 8	Week 91	636	591, 681
Visit 9	Week 104	727	682, 772
Visit x	Every 13 Weeks $13(x-1)$	$7*13*(x-1)-1$ if $x > 1$	Floor ($7*13*(x-1.5)$), Floor ($7*13*(x-0.5)$)-1

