8.3. IGF-1 SDS

A descriptive table including the number and percentages of subjects by visit will be presented where:

- IGF-1 SDS > 2.0
- IGF-1 SDS > 3.0

Listings of IGF-1 and IGF-1 SDS for subjects with abnormally high IGF-1 SDS will be generated.

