9.3. IGF-1 SDS and IGFBP-3 SDS

A descriptive table including the frequency and percentages of subjects at each visit by each group and overall will be presented where:

- IGF-1 SDS < - 2.0
- $0 \leq \text{IGF-1 SDS} \leq 2.0$
- $-2.0 \leq \text{IGF-1 SDS} < 2.0$
- $-1.0 \leq \text{IGF-1 SDS} \leq 2.0$
- IGF-1 SDS > 2.0
- IGF-1 SDS > 3.0

The absolute values and change from baseline at each visit of the IGF-1, IGFBP-3, IGF-1 SDS and IGFBP-3 SDS will be presented with descriptive statistics. Listings will be generated for these outcomes.

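### The pharmacodynamic endpoint, IGF-1 SDS at 5 ± 1 days post-dose, is only listed, and the by-visit IGF-1 tables choose among samples by calendar day without regard to days since dose

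*SAP*

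**What the plan says.** - **Endpoint.** SAP 3.3.3 and Protocol 14.1.3 define one pharmacodynamic endpoint: "Serum IGF-1 SDS at 5 days", plus or minus one day, after the dose. SAP Section 10 repeats the timing ("The Pharmacodynamic (PD) endpoint, Serum IGF-1 SDS will be collected at 5 days", again ± 1 day) and then gives the whole planned output: "Listings will be generated for PD endpoints".
- **Tables.** IGF-1 is tabulated elsewhere. For the cut points > 2.0 and > 3.0, SAP 8.3 says: "A descriptive table including the number and percentages of subjects by visit will be presented where". SAP 9.3 tabulates the proportions in several ranges, including 0 to 2.0, and adds: "The absolute values and change from baseline at each visit of the IGF-1, IGFBP-3, IGF-1 SDS and IGFBP-3 SDS will be presented". Neither section mentions time since dose.
- **Sample selection.** Under SAP 5.3, unscheduled and end-of-study visits are "mapped to the post-baseline scheduled visit with the closest target study day for each scheduled assessment according to Table 2". For duplicates: "After mapping, if there are more than one visit in the same window, the visit closer to the target assessment day will be used". A tie goes to the later visit. All data points are kept only for listings and shift tables.
- **Sampling schedule.** Protocol 10.2 and the Schedule of Events place every post-baseline scheduled visit at 5 ± 1 days post-dose. Protocol 9.6.1 and 9.6.2 give the same timing for the optional repeat IGF-1 test. Protocol 10.2.3 sets no post-dose timing for unscheduled visits.

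**The concern.** The trial times its IGF-1 samples to a fixed point in the weekly dosing cycle, and the pharmacodynamic endpoint is defined by that point. The analysis drops that control. The endpoint as defined appears in no table, and the rule that fills the by-visit tables looks only at study day.

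Samples away from days 4 to 6 are foreseeable from four sources:

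- unscheduled visits prompted by an adverse event, an abnormal laboratory value or a clinical finding (Protocol 10.2.3);
- termination visits, which collect blood after treatment has stopped (Protocol 8.2 and 10.2.4);
- visits that fall in a temporary interruption of treatment, which Protocol 9.6.2 foresees;
- scheduled visits held on the wrong post-dose day, which the SAP keeps unchecked.

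At stake is how the IGF-1 percentages are read. They serve a secondary objective (proportion from 0 to 2.0) and a safety endpoint (> 2.0 and > 3.0). From the planned tables a reader could not tell which values reflect the intended sampling time.

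**Working it through.** **Inputs.** Target days and windows are from SAP 5.3, Table 2. The endpoint window is 4 to 6 days post-dose (5 ± 1). One assumption is added: strict weekly dosing from Day 1, so days since dose = (study day − 1) mod 7.

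**Step 1: reproduce Table 2.** The general row gives target 7·13·(x − 1) − 1 and window Floor(91·(x − 1.5)) to Floor(91·(x − 0.5)) − 1.

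- Visit 3: target 91·2 − 1 = 181; window Floor(136.5) = 136 to Floor(227.5) − 1 = 226. This matches.
- Visits 4 to 9 also match, ending with target 727 and window 682 to 772.
- Visit 2: the target of 90 matches. The formula's lower bound would be Floor(45.5) = 45, but the table extends it to day 2.

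**Step 2: window widths.** Visits 3 to 9: 226 − 136 + 1 = 91 days. Visit 2: 135 − 2 + 1 = 134 days.

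**Step 3: post-dose day at the target.** (90 − 1) mod 7 = 5, and (181 − 1) mod 7 = 5. Each later target is 91 = 13·7 days on, so it also falls 5 days post-dose. The targets are well placed as long as the dosing day never shifts.

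**Step 4: does the window protect the timing?**

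| Window | Days in window | Days at 4–6 post-dose | Other days |
|---|---|---|---|
| Visit 2 | 134 | 57 (42.5%) | 77 |
| Visits 3–9, each | 91 | 39 (42.9%) | 52 |

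These are counts of calendar days that the rule would accept. They are not counts of samples.

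**Step 5: can a correct sample be displaced?** Take Visit 2 (target day 90) and a scheduled sample exactly 5 days post-dose and within the ± 2 week allowance. An unscheduled sample on day d replaces one on day s if |d − 90| < |s − 90|, or if the distances are equal and d is later.

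| Scheduled sample (day s) | Days d that would replace it | Of these, outside 4–6 days post-dose |
|---|---|---|
| 76 | 28 (77 to 104) | 16 |
| 83 | 14 (84 to 97) | 8 |
| 90 | 0 | 0 |
| 97 | 13 (84 to 96) | 8 |
| 104 | 27 (77 to 103) | 16 |

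So the rule as written can discard a sample that meets the endpoint definition in favour of one that does not. The further the scheduled visit lies from its target, the more room there is for this.

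**Step 6: size of bias.** For a proportion such as IGF-1 SDS > 2.0, the error is (share of off-timing samples in the table) × (exceedance probability on time − exceedance probability off time). The documents give neither factor: no off-timing rate and no IGF-1 profile over the dosing week.

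**The case against.** The strongest reply is that timing is already controlled where it matters. Scheduled visits, the optional repeat test and the termination-visit column of the Schedule of Events are all set at 5 ± 1 days post-dose. SAP 5.3 re-maps only unscheduled and end-of-study visits. Unscheduled visits carry focused assessments, so IGF-1 is not routine there, and each subject has at most one termination visit. The trial is descriptive, with no hypothesis test, and IGF-1 SDS is tabulated twice. All of this stands, and it keeps the point small.

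It does not remove the point. A planned sampling day is not a check on the actual day, and nothing in the SAP separates on-time from off-time values in a table.

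Three stronger readings are tempting, and the documents do not support them:

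- *The tables in SAP 8.3 and 9.3 contradict their own endpoints.* They do not. Only the pharmacodynamic endpoint carries the 5 ± 1 day timing; the safety and efficacy IGF-1 endpoints, and IGFBP-3, have none.
- *A 3-day endpoint against a 91-day window measures the error.* It does not. The window assigns visits; it does not decide when blood is drawn.
- *The incidence above 2.0 or 3.0 is understated.* Off-drug samples might read low, but the documents say nothing about values 1 to 3 days post-dose, and visits prompted by abnormal laboratory values could select high ones.

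**Conclusion.** The point holds in a limited form. The pharmacodynamic endpoint as defined is only listed, and the rule that selects samples for the by-visit IGF-1 tables takes no account of days since dose. Followed as written, it can let an off-timing or off-drug sample into those tables, or let one displace a correctly timed sample.

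Most scheduled samples should be on time by design. Exposure is confined to unscheduled draws, termination samples, samples taken during an interruption, and scheduled samples drawn on the wrong post-dose day. How many there will be is unknown, so neither the size nor the direction of any bias can be stated. The day counts above assume strict weekly dosing from Day 1; a shifted dosing day would move the targets off day 5. This is a cheap improvement, not a threat to the trial's conclusions.

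**What to change.** 1. **Derived variable.** For each post-baseline IGF-1 sample, compute days since the last recorded dose. The diary already captures the date and time of each administration (Protocol 9.8 and 11.8).
2. **SAP 5.3.** Where several IGF-1 samples fall in one window, choose first among those 4 to 6 days post-dose, and only then by distance to the target day. If none qualifies, the present rule applies.
3. **SAP Section 10.** Add a by-visit summary of IGF-1 SDS, including the proportions from 0 to 2.0, > 2.0 and > 3.0, restricted to post-baseline samples 4 to 6 days post-dose. Flag the other samples with their post-dose day.
4. **Limits.** Exempt the extension baseline: children from the Genotropin arm were on daily dosing and have no weekly dose to count from at Visit 1. Do not restrict IGFBP-3.
5. **Safety endpoint.** Report the any-sample on-treatment incidence of IGF-1 SDS > 2.0 and > 3.0 alongside, with equal standing, so that no high on-treatment value is lost to the timing rule. State in the SAP what counts as on treatment.

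The cost is one variable from data already collected, one added table, and a slightly smaller n in that table. No trial procedure changes.

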11.1. Preference Questionnaire

The Preference Questionnaire should only be completed for subjects who were treated with daily Genotropin in the prior TransCon hGH CT-301 trial. The parent/legal guardian/caregiver will complete the PQ-P, while the subject, if \geq 9 years old at Visit 1, will complete the PQ-C.

The frequency and percentages will be summarized for each question for PQ-P and PQ-C in tables. Listings will also be provided for PQ-P and PQ-C.

11.2. Child Sheehan Disability Scale

The CSDS is an adaptation of the Sheehan Disability Scale to assess impairment related to childhood anxiety on children and their parents. This measure is being adapted in this trial to assess impairment related to treatment burden on children and their parents/legal guardians/caregivers.

At Visit 1 for all subjects, the parent/legal guardian/caregiver will complete the CSDS-P, while the subject, if \geq 9 years old, will complete the CSDS-C.

Summary score will be the sum of each question score at each visit. It will be calculated based on child and parent separately.

Each question for CSDS-P and CSDS-C at each time point will be summarized. Listings will also be provided for CSDS-P and CSDS-C.

11.3. Convenience & Overall Satisfaction Domains of the Treatment Satisfaction Questionnaire for Medication

At Visit 1, the Convenience and Overall Satisfaction (C&OS) of the Treatment Satisfaction Questionnaire for Medication (TSQM-9) is administered to all subjects.

Only the parent/legal guardian/caregiver will complete the C&OS of the TSQM-9, thus it has been identified for this trial as the C&OS – Parent (C&OS-P).

The study C&OS-P contains two sections including convenience section (item 1-3) and global satisfaction section (item 4-6) on the questionnaires. In order to derive a summary score, the following rules are used.

The convenience score will be set as follows:

- (1) $100 * (\text{sum}(\text{item 1 to 3}) - 3) / 18$, if all the items are presented;
- (2) $100 * (\text{sum}(\text{two items}) - 2) / 12$, if one item is missing,
- (3) Missing if more than one item is missing;

The global satisfaction score will be set as follows:

- (1) $100 * (\text{sum}(\text{item 4 to 6}) - 3) / 14$, if all the items are presented;
- (2) $100 * (\text{sum}(\text{two items}) - 2) / 10$ if item 4 or 5 is missing
- (3) $100 * (\text{sum}(\text{item 4 and 5}) - 2) / 8$ if item 6 is missing
- (4) Missing if more than one more item is missing

Each question for C&OS -P, and the summary score, i.e., convenience score and global satisfaction score, will be summarized at each time point by each group and overall. Listings will also be provided for C&OS -P as well.

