9.9.1.1. Previous hGH Therapies

Subjects who were treated with Genotropin in the prior TransCon hGH CT-301 trial should be instructed NOT to take their regular dose of Genotropin on the day of Visit 1.

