- ³ Medications and health status: Interval history only to be recorded in case of new disease states since the last visit of the prior trial; disease states diagnosed since the initiation of the prior trial (eg, new onset migraines) are medical history; Medical history from the prior trial will be carried forward into this trial's database; Ongoing AEs from the prior trial will be followed until resolution or stabilization; Review of subject diary from the prior trial; Current therapies.
- ⁴ Vital sign measurements include heart rate, blood pressure, respiratory rate and body temperature, which should be performed after the subject has rested for at least 5 minutes.
- ⁵ Height should be measured at each visit at approximately the same time of day, preferably by the same auxologist.
- ⁶ Blood sample collection – A includes IGF-1, IGFBP-3, antibodies against hGH and PEG, and for females of child-bearing potential hCG. If warranted, TransCon hGH, hGH, and PEG serum levels may be analyzed for the interpretation of immunogenicity titers
- ⁷ Blood sample collection – B includes mPEG, hormone/glycemic status (TSH, FT4, FT3, morning cortisol, and HbA1c), chemistry, hematology, and lipid panel. Fasting not required.
- ⁸ Bone age x-ray may not be required at Visit 1 if there is documentation of a bone age x-ray performed within the past 52 weeks. However, if subject's prior documented bone age was > 12.0 years, and it was performed greater than 9 months prior to Visit 1, a bone age x-ray should be performed within approximately 4 weeks of Visit 1. Bone age x-ray may also be performed at any time, if clinically indicated.
- ⁹ Once the GH Auto-Injector is available, transition to the GH Auto-Injector will occur in the US (only) at the next regularly scheduled trial visit when thorough training on preparation and administration will occur.
- ¹⁰ At Visit 1, the C&OS-P, CSDS-P, and CSDS-C should be completed for all subjects.

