- ¹¹ For subjects who were treated with Genotropin in the prior TransCon hGH CT-301 trial, C&OS-P, CSDS-P, CSDS-C, PQ-P, and PQ-C will be completed (as applicable) within the subject diary immediately prior to the 6th dose of investigational product, and in clinic at Visit 2, prior to review of the subject diary, AEs, and concomitant medications. For subjects transitioning to the GH Auto-Injector, C&OS-P, CSDS-P, and CSDS-C will be completed (as applicable) within the subject diary immediately prior to the 6th dose after transition to the GH Auto-Injector, and again in clinic at the following scheduled visit, prior to review of the subject diary, AEs, and concomitant medications. Additionally, for subjects transitioning to the GH Auto-Injector, the DUQ will be completed within the subject diary on the day of the 6th dose of investigational product, and in clinic at Visit 2, prior to review of the subject diary, AEs, and concomitant medications.
- ¹² CSDS-C and PQ-C should only be completed by subjects \geq 9 years old at the time of Visit 1, and/or at the transition to the GH Auto-Injector, as applicable.
- ¹³ Dose adjustments at visits are typically based on subject weight at visits. However, dose adjustments may occur between visits per Section 9.6.
- ¹⁴ Local tolerability assessment at the injection site to be performed at time of injection, and by the trial staff at visits.
- ¹⁵ Investigational product compliance includes review of subject diary and returned investigational product.
- ¹⁶ AE review includes review of subject diary and physical examination of injection sites. AEs that are considered mild and not related to investigational product will not be reported on the AE CRF. AEs reported up to 14 days after the final dose of TransCon hGH will be captured.

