Instructions: Please take some time to think about your level of satisfaction or dissatisfaction with the medication your child is taking in this clinical trial. We are interested in your evaluation of the convenience of the medication and your overall satisfaction with the medication over the last two to three weeks or since your child last used it.	
For each question, please place a single check mark next to the response that most closely corresponds to your own experiences.	
1. How easy or difficult is it to use the medication in its current form?	
 ₁ Extremely Difficult	
 ₂ Very Difficult	
 ₃ Difficult	
 ₄ Somewhat Easy	
 ₅ Easy	
 ₆ Very Easy	
 ₇ Extremely Easy	
2. How easy or difficult is it to plan when your child will use the medication each time?	
 ₁ Extremely Difficult	
 ₂ Very Difficult	
 ₃ Difficult	
 ₄ Somewhat Easy	
 ₅ Easy	
 ₆ Very Easy	
 ₇ Extremely Easy	
3. How convenient or inconvenient is it to take the medication as instructed?	
 ₁ Extremely Inconvenient	
 ₂ Very Inconvenient	
 ₃ Inconvenient	
 ₄ Somewhat Convenient	
 ₅ Convenient	
 ₆ Very Convenient	
 ₇ Extremely Convenient	

enliGHten Visit ____

ID #

C&OS-PARENT (Continued)

4. Overall, how confident are you that taking this medication is a good thing for your child?

- ₁ Not at All Confident
- ₂ A Little Confident
- ₃ Somewhat Confident
- ₄ Very Confident
- ₅ Extremely Confident

5. How certain are you that the good things about your child's medication outweigh the bad things?

- ₁ Not at All Certain
- ₂ A Little Certain
- ₃ Somewhat Certain
- ₄ Very Certain
- ₅ Extremely Certain

6. Taking all things into account, how satisfied or dissatisfied are you with this medication?

- ₁ Extremely Dissatisfied
- ₂ Very Dissatisfied
- ₃ Dissatisfied
- ₄ Somewhat Satisfied
- ₅ Satisfied
- ₆ Very Satisfied
- ₇ Extremely Satisfied

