3.3.4. Other Endpoints

- Preference for weekly TransCon hGH or daily Genotropin treatment
- Satisfaction with weekly TransCon hGH

4. Analysis and Reporting

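### The overall row for the C&OS-P and CSDS questionnaires cannot be read across time points, because both the drug rated and the set of respondents change after Visit 1

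*SAP*

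**What the plan says.** **Who answers, and when.** Protocol 18.2, note 10: "At Visit 1, the C&OS-P, CSDS-P, and CSDS-C should be completed for all subjects". Note 11 limits the repeats at Week 6 (in the diary before the 6th dose) and Visit 2: "For subjects who were treated with Genotropin in the prior TransCon hGH CT-301 trial, C&OS-P, CSDS-P, CSDS-C, PQ-P, and PQ-C will be completed". It adds one other set of respondents: "For subjects transitioning to the GH Auto-Injector, C&OS-P, CSDS-P, and CSDS-C will be completed (as applicable) within the subject diary". These answer before the 6th dose after transition and at the following scheduled visit. Device transition is in the US only, and no number is given.

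**What is rated.** The C&OS-P in Protocol Appendix 5 asks about "your overall satisfaction with the medication over the last two to three weeks or since your child last used it". Protocol 9.9.1.1 shows that the CT-301 Genotropin group is on daily Genotropin up to Visit 1: these subjects "should be instructed NOT to take their regular dose of Genotropin on the day of Visit 1". The CSDS-P in Appendix 4 asks about current interference from treatment.

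**What is planned.** SAP 11.3 has each C&OS-P question and the "convenience score and global satisfaction score, will be summarized at each time point by each group and overall". SAP 11.2 says only that the CSDS questions are summarised at each time point, but SAP 5 presents all summaries both overall and by rollover group. SAP 3.3.4 names the endpoint as "Satisfaction with weekly TransCon hGH", and SAP 2.2 sets the objective as satisfaction with weekly treatment over time. SAP 5 provides change from baseline where applicable; SAP 11.2 and 11.3 do not mention it.

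**The concern.** A reader who wants satisfaction with TransCon hGH over time will naturally look at the overall row. At Visit 1 that row averages ratings of two drugs. At Week 6 and Visit 2 it describes a much smaller set of families, chosen because they had been on the other drug or had changed device. A difference between the rows therefore mixes a change in opinion with a change in who was asked and what they were rating. The same holds for treatment burden on the CSDS. At stake is how a secondary objective is reported, not the primary safety objective.

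**Working it through.** **Inputs from the documents.** CT-301: about 150 children, randomised 2:1 to TransCon hGH or Genotropin. CT-302: about 150, all on TransCon hGH (both Protocol 5.3). Planned size: about 300 (Protocol 8); SAP 3.2 still says about 400.

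**Planned size.** 150 + 150 = 300, which reproduces the protocol's figure but not the SAP's 400.

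**Composition, assuming full rollover.**
- Rating Genotropin at Visit 1: 150 × 1/3 = 50.
- Rating TransCon at Visit 1: 100 + 150 = 250.
- Genotropin share of the overall row at Visit 1: 50/300 = 16.7%.
- Expected at Week 6 and Visit 2, before device switchers: the same 50.

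**Effect on the overall trend, before device switchers.** Let T be the mean TransCon rating and G the mean Genotropin rating at Visit 1, and S the switchers' mean later, on TransCon.
- Overall mean at Visit 1 = (250T + 50G)/300 = (5T + G)/6.
- Overall trend = S − (5T + G)/6.
- Within-child change = S − G.
- Overall trend minus within-child change = G − (5T + G)/6 = −(5/6)(T − G).

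The distortion is thus 5/6 of the gap between the two drugs' Visit 1 ratings. For the C&OS-P (higher is better):
- T = G: no distortion.
- T above G: the trend is shifted down. A true gain is attenuated, and it changes sign if it is smaller than 5/6 (83%) of T − G.
- T below G: the trend is shifted up, so a true gain is exaggerated.

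**Illustrations.** All scores are assumed.

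| Scale | T | G | S | Overall at Visit 1 | Overall trend | Within-child change |
|---|---|---|---|---|---|---|
| C&OS-P (0–100) | 80 | 60 | 80 | 76.67 | +3.33 | +20 |
| C&OS-P | 80 | 60 | 78 | 76.67 | +1.33 | +18 |
| C&OS-P | 80 | 60 | 75 | 76.67 | −1.67 | +15 |
| C&OS-P | 80 | 60 | 70 | 76.67 | −6.67 | +10 |
| C&OS-P | 70 | 70 | 75 | 70.00 | +5.00 | +5 |
| CSDS-P (0–50, lower is better) | 3 | 10 | 5 | 4.17 | +0.83 | −5 |

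**Sensitivity to rollover.** The reversal threshold is 1 minus the Genotropin share.
- SAP's 400 with 50 on Genotropin: 50/400 = 12.5%, threshold 87.5%.
- 80% of the Genotropin group and all others: 40/290 = 13.8%, threshold 86.2%.
- All of the Genotropin group and 80% of the others: 50/250 = 20%, threshold 80%.

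**Device switchers.** Take T = 80, G = 60, S = 75 and add 25 to 75 device switchers with means of 75 to 85. The overall trend then runs from −1.67 to +4.33. At the upper end the later mean is (50 × 75 + 75 × 85)/125 = 81.0, and 81.0 − 76.67 = +4.33. The switchers' own change stays at +15. Device scores fall at study Week 6 and Visit 2 only for children who transition at Visit 1. Later transitions give scores at later visits, and the SAP does not say how these are placed in time.

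**The case against.** The sentence that creates the overall row also creates the by-group rows, and SAP 3.1 defines the CT-301 Genotropin subjects as their own group. In the illustration with G = 60 and S = 75, that group's row would show 60 and then 75, which is the right answer printed beside the overall figure. This stands: a reader might infer that the plan reports no valid trend, but the Genotropin-group row is usable if device-transition scores are kept out of it.

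Change from baseline is also available. SAP 5 allows it, Table 3 defines it, and SAP 5.1 sets the extension baseline for most endpoints. That would give the paired change. It stands in part: the where-applicable qualifier leaves the matter open. The SAP names change explicitly for laboratory values, vital signs, bone age, height SDS and IGF-1, but not for these questionnaires.

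The SAP is not unaware that daily treatment is being rated; the opening of SAP 11 lists satisfaction with daily hGH as well as weekly TransCon hGH. SAP 5 also reports n, so a fall from about 300 to about 50 would be visible. Both points are fair, but neither makes the overall row interpretable.

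A reader might also take the Visit 1 to Visit 2 scores as the only within-family comparison of the two drugs. They are not: the Preference Questionnaire asks the same families to compare weekly with daily injections and has its own analysis in SAP 11.1.

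**Conclusion.** The overall row for the C&OS-P and CSDS is not interpretable across time points and should not be shown as a trend. The change in respondents and in the drug rated follows directly from the documents. The 17% share and the fall to about 50 rest on full rollover and the planned sizes of the prior trials. They do not carry over to the CSDS-C, which is limited to children aged 9 or older.

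It would be tempting to conclude that the plan will report a reversed effect. The documents do not support that, because they give no C&OS-P or CSDS means. For the C&OS-P, before device switchers, reversal of a true gain needs TransCon to be rated above Genotropin at Visit 1 and switchers to gain less than about 83% of that gap (80% to 88% under the other rollovers tried). Otherwise the trend is attenuated, exaggerated or, with equal ratings, undistorted. The fault is confined to the overall row, provided device-transition scores are separated.

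**What to change.** In SAP 11.2 and 11.3:

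1. Drop the overall row for the C&OS-P and CSDS across time points, or restrict it to subjects with paired scores.
2. At Visit 1, label and present Genotropin ratings (CT-301 Genotropin group) separately from TransCon ratings (CT-301 TransCon group and CT-302).
3. State that the change from baseline in SAP 5 and Table 3 applies to these scores in the CT-301 Genotropin group, as a paired change from Visit 1 to Week 6 and to Visit 2. This is the contrast on switching drug.
4. Add the paired Week 6 to Visit 2 change in the same group, which addresses satisfaction while on TransCon hGH over time.
5. Summarise device-transition questionnaires separately, by time since transition.

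A confidence interval on the paired changes would help, but in a descriptive trial it is a matter of choice.

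The cost is SAP wording and table shells, with no new data. The drawback is that the over-time result rests on about 50 subjects rather than about 300, and the on-TransCon part spans nominally 13 − 6 = 7 weeks. When the SAP is revised, its planned size of 400 should be aligned with the protocol's 300.
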